14.2.4 Quality assurance

Outcome data are input directly and stored in the REDCap database.

14.2.5 Archiving - Data and document retention

The data will be archived and retained until the oldest infant reaches 25 years, as per guidance for clinical trials.

At the end of the trial period, data will be archived via two means:

Electronic data (e.g., fNIRS raw data, and REDCap data) will be stored on a secure server at the Bionics Institute, which is backed up nightly.

Hard copy laboratory notebooks will be stored in a locked filing cabinet in the dedicated archive space at the Institute, clearly labelled with clinical trial dates and titles for easy retrieval if necessary. After the time period when the data may want to be reused for research has elapsed, the hard copy lab notebooks will be scanned and included in the digital archive until the 25 years is complete.

The consent forms will also be scanned and included in the trial archive. The trial re-identification document matching trial IDs to personal IDs will be stored in the archive along with the other documents but will be password protected. The long-term custodian of the archive (the person in the role of Chief Technology Officer/Head of Research Operations) will retain the password to re-identify the data in the 25-year period.

Records will not be destroyed without the written consent of the Sponsor Investigator / Site Principal Investigator. It is not intended that the electronic data be destroyed at the end of the archive period. However, the re-identification document will be deleted using secure deletion software.

14.2.6 Data sharing

Beginning 1 month following the end of the trial, the following will be made available long-term for use by future researchers from a recognised research institution whose proposed use of the data has been ethically reviewed and approved by an independent committee and who accept Bionics Institute's conditions for access:

- Individual participant raw fNIRS data (prior to processing) after de-identification
- Trial stimulus presentation protocol

15 TRIAL OVERSIGHT

15.1 Governance structure

The Principal Investigator is responsible for supervising any individual or party to whom they have delegated tasks. They will provide continuous supervision and documentation of their oversight. As part of meeting this GCP requirement, the project's clinical team, made up of the PI and research audiologists, one of whom is the trial coordinator, will act as the trial management group (TMG). The TMG will provide close oversight over all aspects of the trial, ensuring that there is a forum for identifying and addressing issues. The TMG will formally and regularly review and evaluate the accumulated trial data for participant safety, device deficiencies, trial conduct and progress, and make determinations under the PI concerning the continuation, modification, or termination of the trial.

15.2 Site Monitoring

Trial site monitoring is conducted to ensure that the rights and well-being of trial participants are protected, that the reported trial data are accurate, complete, and verifiable, and that the conduct of the trial complies with the currently approved protocol and amendment(s), good clinical practice, and applicable regulatory requirements.

Monitoring for this trial is the responsibility of the sponsor and will be performed onsite by the Bionics Institute's Research Governance Office. The monitor will compare the trial processes and documentation with the trial protocol and the requirements of ICH-Good Clinical Practice (GCP) and ISO 14155 (ISO) guidelines, with an emphasis on critical data and processes for the specific trial. This will include review of signed consent forms and the consent process, safety events and data related to the primary outcome.

The extent and frequency of monitoring will be detailed in the trial Monitoring Plan. The monitoring schedule may be revised if recruitment is slower or faster than expected, requested by the sponsor in response to any issues arising, or if there is an elevation or reduction in the risk profile of the trial.

The research team will provide direct access to all trial related sites, source data/documents, and reports for the purpose of monitoring and auditing by the sponsor, and inspection by local and regulatory authorities.

15.3 Quality Control and Quality Assurance

The Principal Investigator has responsibilities in relation to quality management, including the development of SOPs that identify, evaluate and control risk for all aspects of the trial, e.g., trial design, source data management, training, eligibility, informed consent, and adverse event reporting. The Principal Investigator will also implement quality control (QC) procedures, which will include the data entry system and data QC checks. Any missing data or data anomalies will be communicated to the relevant trial personnel for clarification/resolution.

As outlined in the previous section (Site Monitoring), the trial monitor will verify that the clinical trial is conducted and data are generated, documented (recorded), and reported in compliance with the protocol, good clinical practice, and applicable regulatory requirements.

In the event of non-compliance that significantly affects human participant protection or reliability of results, the Sponsor will perform a root cause analysis and corrective and preventative action plan

(CAPA) in collaboration with the Principal Investigator. This will be entered into the Bionics Institute's Quality Management System.

16 STATISTICAL METHODS

16.1 Sample Size Estimation

NA. We propose that 10 infants are sufficient to establish safety and preliminary evidence for functionality as detailed in Section 16.3. As this is primarily a safety study and only preliminary confirmation of functionality is evaluated, statistical analysis is not appropriate.

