8 TRIAL OBJECTIVES AND OUTCOMES

8.1 Objectives

8.1.1 Primary objective

The primary objective of this trial is to establish the safety and comfort of EarGenie MVP.

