12.5.2 Withdrawal of consent - participant withdraws from all trial participation

Participants are free to withdraw from the trial at any time upon their request or the request of their legally acceptable representative.

The data from infant participants who have completed all of the fNIRS testing when their parent/guardian withdrew consent will be included in the trial unless the parent/guardian asks us not to use the data.

A dedicated Case Report Form will be used to capture the date of participant withdrawal of consent.

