12.5.4 Replacements

Infant participants who withdraw from the trial at any time before or during fNIRS testing can be replaced.

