12.5.5 Trial Closure

An infant participant is considered to have completed the trial when partial or complete fNIRS test results have been obtained in one test session.

The end of the trial is defined as completion of fNIRS tests on 10 infants. At this stage, the Sponsor-Investigator will ensure that all HRECs and RGOs as well as all regulatory and funding bodies have been notified.

This trial may be temporarily suspended or prematurely terminated if there is sufficient reasonable cause. If the trial is prematurely terminated or suspended, the Sponsor-Investigator will promptly inform trial participants, HREC and RGO, the funding (where applicable) and regulatory bodies, providing the reason(s) for the termination or suspension. Circumstances that may warrant termination or suspension include, but are not limited to:

- Determination of an unexpected, significant, or unacceptable risk to participants that meets the definition of a Significant Safety Issue (SSI) (for the definition refer to Section 8.1).
- Insufficient compliance to protocol requirements
- Data that are not sufficiently complete and/or evaluable
- Determination of futility

In the case of concerns about safety, protocol compliance or data quality, the trial may resume once the concerns have been addressed to the satisfaction of the sponsor, HREC, RGO, funding and/or regulatory bodies.

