16.2 Population to be analysed

All infants in the study.

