16.2.1 Handling of missing data

NA. There is only one test session and if a parent withdraws before or during the session, we will replace that infant with another.

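### Section 16.1 says ten infants suffice to establish safety, but 0/10 leaves per-infant rates up to 25.9% (one-sided 95%) or 30.8% (two-sided 95%) open, and the primary incidence has no consistent denominator

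*Combined protocol and SAP*

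**What the plan says.** On sample size, 16.1 enters NA and then asserts: "We propose that 10 infants are sufficient to establish safety and preliminary evidence for functionality as detailed in Section 16.3". It adds that "statistical analysis is not appropriate". Section 8.1.1 reads "The primary objective of this trial is to establish the safety and comfort of EarGenie MVP", and the synopsis, 6.1 and 8.2 word the primary aim the same way. The functionality aim, which rests on the same ten infants, is worded as preliminary.

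The primary measure (8.2) is the incidence of adverse events and of discomfort, and discomfort includes crying, pulling at the headgear and skin marks. Section 16.3 reports incidence, duration and a narrative of each incident, without intervals.

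Several sections bear on who is counted:

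- 16.2: "All infants in the study".
- 16.3: safety recording is described for ten test sessions.
- 16.2.1: "if a parent withdraws before or during the session, we will replace that infant with another".
- 12.5.4: "Infant participants who withdraw from the trial at any time before or during fNIRS testing can be replaced".
- 12.5.2: "The data from infant participants who have completed all of the fNIRS testing when their parent/guardian withdrew consent will be included in the trial". A parent or guardian can ask otherwise.
- 12.5.5: "An infant participant is considered to have completed the trial when partial or complete fNIRS test results have been obtained in one test session". The same section ends the trial once ten infants have been tested.
- Synopsis and 5.3: the trial lasts six months or until ten infants are tested, whichever is shorter.

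**The concern.** To establish safety is a stronger claim than ten infants can support, and it is made for the primary outcome. Section 21 says the results will be posted on the trial registry, not published in a journal, and will be used to support further trials. Later readers will therefore rely on the reported incidence and the count beneath it.

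The denominator matters because the outcome and the reasons for leaving overlap. Under 13.1.1 significant distress is an adverse event. Under 7.1 testing stops if a distressed infant cannot be resettled, and under 9.8 a parent may stop at any stage. The infants most likely to leave part-way are plausibly those with an event. A rule that replaces them without fixing their place in the count can lower the reported incidence but cannot raise it.

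**Working it through.** **The plan's own figure.** There is none to reproduce. Ten is stated without a target rate, confidence level or precision. The 95% level below is an assumption, since the documents set none. Zero events is taken as the most favourable possible result.

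**Upper limit for zero events in n infants (exact binomial).** Solve (1 − p)^n = a, which gives p = 1 − a^(1/n).

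- One-sided 95%: 1 − 0.05^(1/10) = 0.2589.
- Two-sided 95%: 1 − 0.025^(1/10) = 0.3085.
- If only nine were tested: 1 − 0.05^(1/9) = 0.2831 one-sided.
- Wilson limits, z²/(n + z²), for comparison: 21.3% one-sided and 27.8% two-sided. The conclusion is the same.
- Chance of seeing no event at a true 10% rate: 0.9^10 = 0.349.

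**Who is counted.** Take an infant whose parent withdraws part-way, in distress, after some results have been obtained.

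- 16.2 read alone: counted.
- 16.3 read as ten sessions: counted only if this session is one of the ten.
- 12.5.2: silent, because it speaks only of infants who finished all testing.
- 12.5.5: has completed the trial, because partial results exist.
- 12.5.4: may be replaced. 16.2.1: will be replaced.

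The same infant can thus be both a completer and a replaced withdrawal. If a tester stops the session for distress (7.1), nothing says whether that is a withdrawal or leads to replacement.

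**What the choice does to the result (Clopper-Pearson).** For x events in n infants, the two-sided limits are the 0.025 quantile of Beta(x, n − x + 1) and the 0.975 quantile of Beta(x + 1, n − x). The lower limit is 0 when x = 0.

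| Reported as | Incidence | Two-sided 95% CI |
|---|---|---|
| 0/10 | 0% | 0% to 30.8% |
| 1/10 | 10% | 0.3% to 44.5% |
| 1/11 | 9.1% | 0.2% to 41.3% |
| 2/12 | 16.7% | 2.1% to 48.4% |

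One infant withdrawn in distress and replaced, with no other event, is 1/11 if counted and 0/10 if not. Two such infants are 2/12 if counted and still 0/10 if not.

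**Response proportions.** These are also reported without intervals. Results that just meet the stated expectations would give 9/10 (55.5% to 99.7%) and 7/10 (34.8% to 93.3%).

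**The case against.** The design is a small descriptive first-in-human study, and description suits it. No acceptable event rate is stated, so an upper limit of 26% or 31% fails no criterion in the protocol. The outcome mixes crying and skin marks with other adverse events, so an open rate of that size is not a rate of serious harm. The safety case also draws on over 100 babies tested with the research device (7.1) and on long fNIRS use and design mitigations (13). All of this stands, but none of it makes ten infants enough to establish the safety and comfort of this device.

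On the denominator, a reader might infer that a distressed infant's event would vanish from the report. The documents do not support that. Section 16.2 excludes nobody. Section 12.3 has every Case Report Form summarised in the safety report, and 13.2 and 13.3 require adverse events to be captured and recorded. A plain reading keeps the event in the narrative, and probably the infant in the population. What remains open is whether that infant enters the reported numerator and denominator, because 12.5.2 and 16.3 can be applied the other way.

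A shortfall below ten is also uncertain. Sections 5.3 and 12.5.5 give different end points, and 9.7 expects no difficulty in recruiting.

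**Conclusion.** The point holds as a claim that outruns the design and as a counting rule that is not settled. Ten infants with no events would exclude per-infant rates above 25.9% (one-sided) or 30.8% (two-sided), and nothing lower. If an infant withdrawn in distress were replaced and left out, 9.1% would be reported as 0%, so the error would run towards reassurance on the primary outcome. Whether that would happen depends on how the sections are read.

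The figures assume a 95% level, exact binomial limits, independent infants and at most one count per infant.

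A reader might also infer that the sample size was miscalculated or that more infants are needed. Neither follows: 16.1 offers no calculation, and the number suits a preliminary study described as one. The change is worth making, but it does not call the design into question.

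**What to change.** 1. **16.1.** Replace the claim of sufficiency with: sufficient to give preliminary safety information; 0 events in 10 infants would exclude true per-infant rates above about 26% (one-sided 95%) or 31% (two-sided 95%), recalculated for the number actually tested. Replace "statistical analysis is not appropriate" with: no hypothesis test is planned; results are descriptive with exact 95% confidence intervals. Align the primary-aim wording in the synopsis, 6.1, 8.1.1 and 8.2.
2. **16.2.** Define the safety set as every infant who starts any study procedure in the session. Otoscopy and tympanometry come before headgear placement (12.3), and 13.1.1 counts procedure-related events as adverse events. Define the headgear discomfort set as every infant on whom the headgear was placed. Both sets keep infants whose session stops early or who withdraw and are replaced, unless the parent or guardian asks that the data not be used; report how many were removed for that reason.
3. **Reconciliation.** Bring 12.5.2, 12.5.4, 12.5.5 and 16.2.1 into line with these sets, and state whether a tester's stop for distress counts as a withdrawal. Reconcile the six-month limit (synopsis, 5.3) with the ten-infant end of trial (12.5.5).
4. **16.3.** Report numerator, denominator and exact 95% interval for infants with any adverse event, infants with any discomfort, and each response proportion. Keep the durations and narratives. The first two counts overlap by definition, so show them side by side and do not add them.

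The cost is a few sentences, a few exact intervals and an amendment through the ethics committee, because keeping data from infants withdrawn part-way must agree with the consent form. The stated conclusion becomes less favourable. No infants or visits are added, and the response expectations stay as they are.

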16.2 Population to be analysed

All infants in the study.

16.2.1 Handling of missing data

NA. There is only one test session and if a parent withdraws before or during the session, we will replace that infant with another.

16.3 Methods of analysis

Safety analysis: A careful recording during all of the 10 test sessions of any signs of discomfort from the infant, along with any parent reports of such discomfort within 48 hours of the test, will be noted on Case Report Forms and collated and summarised at the end of the study. Any adverse events will be recorded and managed as per Section 13. The data will be presented as incidence of such events along with their duration, and a full description of each incident.

To obtain preliminary evidence of the functionality of the EarGenie MVP, the automatic reports generated by EarGenie MVP, which includes the test result and the average haemodynamic response waveforms related to that test, will be examined. We expect infants with normal hearing to be able to both hear the speech sounds and to be able to discriminate them. Therefore, we expect a majority of infants to return a positive test result (as in our previous research with the NIRx system), and that the waveforms generated should have characteristics in common with what we expect from our previous research. These data will be summarised as proportions of infants for whom the EarGenie MVP test showed a) a significant detection, and b) a significant discrimination as detailed below.

Specifically, we expect that at least 9/10 infants will show a significant detection response for "Ba" at 65 dB SPL, and that their average waveforms for this test should consist of a positive HbO peak around 5-8 s latency, or a negative HbO response with latency 12-16 s, or a shape consistent with a combination of these shapes (refer to Figure 1).

For the test of discrimination of "Ba" from "Ga", we expect that at least 7/10 infants will show a significant discrimination response, and that their average response waveforms should consist of a positive HbO response with latency 6-12 s or a negative HbO response with latency 12-20 s, or a combination of both these shapes (Figure 2).

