Figure 1 Average response waveforms in left and right temporal areas (LT, LR) and left and right prefrontal areas (LPF, RPR) in response to detection of “Ba” at 65 dB SPL. The grey shaded region is the duration of the stimulus in the silence baseline.

[figure not shown]

Figure 2 Average waveforms of responses (changes in HbO (solid) and HbR (dotted)) to discrimination of “Ba” from “Tea”, “Bee”, and “Ga”. Grey shaded region is the duration of the novel stimulus in the non-silence baseline.

Given the success of our development of this fNIRS test, we have built a prototype system (EarGenie MVP) that can automatically run the tests and generate results so that clinicians can easily perform the tests. In this clinical trial, we aim to confirm its safety and basic functionality before performing further clinical studies and trials with EarGenie MVP. The Investigator Brochure outlines how EarGenie MVP functions, is designed, and its safety features.

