8.2 Outcomes

Table listing objectives and outcomes.

OBJECTIVE	OUTCOME & OUTCOME MEASURE
Primary	
The primary objective of this trial is to establish the safety and comfort of EarGenie MVP.	The intended outcome is that EarGenie MVP is safe and comfortable for use in human infants. The measure is the incidence of any adverse events recorded (safety) and incidence of discomfort. The measures of discomfort will include observations of crying, attempts to remove headgear, verbal indications of distress (in an infant with developed speech), and observations of any marks left by the headgear on the skin, along with the duration (in minutes) of such incidents. The summary report will be presented as incidence of such events along with their duration, and a full description of each incident.
Secondary	
The secondary objective of this trial is to obtain preliminary evidence of device feasibility by showing that the test results obtained when using EarGenie MVP to test normally-hearing infants are largely consistent with those obtained by a cohort of 36 normally-hearing infants previously tested in our lab with the NIRx NIRScout continuous wave near infrared spectrometer.	The secondary outcome is that the test results obtained with EarGenie MVP are largely consistent with the sensitivity and specificity of the test results formerly obtained with our NIRx NIRScout research device in normal-hearing infants, thus confirming the suitability of EarGenie MVP for further clinical studies. The outcome measure is the proportion of babies who show a significant detection and discrimination response and also produce fNIRS average waveforms with shape consistent with those shown in the previous studies. Specifically, we expect that at least 9/10 infants (90%) will show a significant detection response for “Ba” at 65 dB SPL, and that their average waveforms for

OBJECTIVE	OUTCOME & OUTCOME MEASURE
	
this test should consist of a positive HbO peak around 5-8 s latency, or a negative HbO response with latency 12-16 s, or a shape consistent with a combination of these shapes (refer to Figure 1).
 
For the test of discrimination of “Ba” from “Ga”, we expect that at least 7/10 infants (70%) will show a significant discrimination response, and that their average response waveforms should consist of a positive HbO response with latency 6-12 s or a negative HbO response with latency 12-20 s, or a combination of both these shapes (Figure 2).

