20 FINANCIAL DISCLOSURE AND CONFLICTS OF INTEREST

Investigators will declare any conflict of interest or financial interest related to this trial. These will be recorded on the Bionics Institute Conflict of Interest (COI) register and managed by the Bionics Institute consistent with their COI policy. Notifications of relevant conflicts of interest will be submitted to journals when requesting publication. Bionics Institute/Researchers [name], [name], [name], and [name] hold patents in relation to the methods used to measure sound discrimination and detection from fNIRS data.

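### The waveform part of the secondary outcome is judged from a report that also shows the device's verdict, with no fixed scoring rule; separately, no NIRx conformity rate is given to compare it with

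*Combined protocol and SAP*

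**What the plan says.** The synopsis (Section 2) and Section 8.2 define the secondary measure as the proportion of infants with a significant response who meet a second condition: "and also produce fNIRS average waveforms with shape consistent with those shown in the previous studies".

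Section 16.3 describes the assessment. The automatic report, "which includes the test result and the average haemodynamic response waveforms related to that test, will be examined". The same paragraph states the expected finding, that "the waveforms generated should have characteristics in common with what we expect from our previous research". The shape criteria are:

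- Detection: "a positive HbO peak around 5-8 s latency, or a negative HbO response with latency 12-16 s, or a shape consistent with a combination", with a pointer to Figure 1.
- Discrimination: "a positive HbO response with latency 6-12 s or a negative HbO response with latency 12-20 s, or a combination of both these shapes", with a pointer to Figure 2.

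The caption to Figure 1 in Section 6.2 describes "Average response waveforms in left and right temporal areas (LT, LR) and left and right prefrontal areas". The criteria do not choose among these regions.

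For the NIRx reference, Section 6.2 gives sensitivities of 97% (detection) and 78% (discrimination), each with specificity of 100%. These describe the test result. On shape, Section 9.1 says only that the responses of the 36 NIRx infants were predictable and did not differ by age or between infants.

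Section 11.1 rules out blinding for infants and parents and is silent on whoever reads the waveforms. Section 14.2.3 gives analysts coded data, which hides identity but not the device's verdict.

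**The concern.** The waveform requirement is the part of the secondary outcome that could show the device is recording a recognisable haemodynamic response, and not merely that its algorithm returned a positive result. It can do this only if the shape is judged by a rule that does not depend on the algorithm's answer.

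As written, the verdict and the trace arrive on one report, the expected shape is announced in advance, and the criterion has room to stretch. The detection peak need only be *around* its window, either polarity is acceptable, a combined shape is acceptable but undefined, no region is named, and no minimum deflection is set. Two readers could classify the same trace differently, and a reader who knows the verdict may lean towards agreeing with it.

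A second and separate gap is that the aim is consistency with NIRx, yet no figure says how many NIRx infants met these windows individually. Even a perfectly objective EarGenie conformity rate would have nothing to be set against.

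**Working it through.** **1. The plan's own figures.** The documents contain no calculation to reproduce: Section 16.1 declines a sample-size estimate, and the benchmarks are at least 9/10 (detection) and at least 7/10 (discrimination). They can be checked against the NIRx test-result rates, treating 10 infants as independent.

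- Detection, p = 0.97: P(X ≥ 9) = 10 × 0.97⁹ × 0.03 + 0.97¹⁰ = 0.228 + 0.737 = 0.965.
- Discrimination, p = 0.78: P(X ≥ 7) = Σ C(10,k) × 0.78ᵏ × 0.22¹⁰⁻ᵏ for k = 7 to 10 = 0.841.

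The benchmarks fit the NIRx rates for significance alone. They leave no allowance for waveforms that fail.

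**2. If the benchmarks count result plus waveform.** Let c be the share of significant infants whose waveform conforms. The documents give no value, so c is an assumption. The combined rate is 0.97c or 0.78c, and the same binomial tails give:

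| c | P(≥ 9/10), detection | P(≥ 7/10), discrimination |
|---|---|---|
| 1.00 | 0.965 | 0.841 |
| 0.95 | 0.818 | 0.754 |
| 0.90 | 0.631 | 0.655 |
| 0.80 | 0.308 | 0.444 |

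On this reading the missing conformity rate matters a good deal. If the benchmarks count the test result alone, the waveform read does not enter them. Section 16.3 tabulates only significant detection and discrimination, and the synopsis limits count only absent responses (1/10 and 3/10), whereas the measure in Section 8.2 requires both conditions. The text does not settle which applies.

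**3. How far a lenient read can move the result.** Suppose the reader accepts a fraction f of non-conforming waveforms. Effective conformity is c′ = c + (1 − c)f, which cannot exceed 1. With c = 0.80 and f = 0.5 (both assumed), c′ = 0.80 + 0.20 × 0.5 = 0.90. The chance of meeting the benchmark then moves from 0.308 to 0.631 (detection) and from 0.444 to 0.655 (discrimination). With f = 1 it reaches the first row of the table and stops there. The combined proportion is therefore capped at the automated significance proportion, and at that cap the waveform adds nothing to the test result.

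**4. How permissive the windows are: single-region illustration only.** Assume a trace without a response whose maximum and minimum fall at independent, uniform times in an epoch of L seconds. Neither L nor this model comes from the documents. Window widths are 8 − 5 = 3 s and 16 − 12 = 4 s for detection, and 12 − 6 = 6 s and 20 − 12 = 8 s for discrimination. The chance of meeting either window is 1 − (1 − w₁/L)(1 − w₂/L).

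- L = 20 s: detection 1 − 0.85 × 0.80 = 0.32; discrimination 1 − 0.70 × 0.60 = 0.58.
- L = 30 s: detection 1 − 0.90 × 0.867 = 0.22; discrimination 1 − 0.80 × 0.733 = 0.41.

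These figures describe how selective the windows are on their own. They are not rates of false success, because the infant must also have a significant result.

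**The case against.** The best defence is that the outcome is conjunctive and the first condition is automated. A reader cannot turn a non-significant infant into a success, and with a reported NIRx specificity of 100% a response-free trace should seldom reach the stage where shape matters. That stands, and it sets the ceiling in step 3.

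Polarity and latency windows are also prespecified and tied to figures, so the read is not unstructured. That stands too. The figure images could not be inspected here and may show region-specific shapes, but the written criterion selects no region.

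Several stronger readings are tempting and are not supported:

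- **Any of four regions may qualify, so almost any trace conforms.** With four independent regions, the 20 s figures would become 1 − 0.68⁴ = 0.79 and 1 − 0.42⁴ = 0.97. No passage permits any region to count. Four regions appear only in the detection caption; the discrimination caption names none. Signals from one infant's head need not be independent.
- **The waveform is half of the outcome.** It is one of two required conditions, and no weighting is stated.
- **The read is biased.** Bias is a risk that follows from an unmasked, unscored read; it is not documented. Section 20 discloses that the institute or its researchers "hold patents in relation to the methods used to measure sound discrimination and detection from fNIRS data" and says conflicts are managed under policy. Nothing says a patent holder reads the waveforms, or that the verdict is seen first.
- **The missing NIRx rate results from the unmasked read.** It is a separate gap. Section 9.1 does offer a qualitative reference, but that is not a rate.

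It can also be said that naming a region and removing the visual read is not enough, since one region still conforms by chance in step 4. That is correct, and it is why the rule needs a minimum response size and a definition of a combined shape.

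**Conclusion.** The point holds in limited form. The secondary outcome requires a conforming waveform, but Section 16.3 supplies neither a reproducible rule nor separation from the verdict, and the documents give no NIRx conformity rate. The waveform element therefore adds little independent evidence beyond the automated result, and consistency of shape with NIRx cannot be measured.

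The effect is bounded: the combined proportion cannot exceed the automated significance proportion. Within that bound, if the benchmarks include the waveform, the chance of meeting them at NIRx test-result rates runs from 0.965 down to 0.308 (detection) and from 0.841 down to 0.444 (discrimination) as assumed conformity falls from 1.00 to 0.80. The single-region figures in step 4 are illustrative and depend on the assumed epoch and uniform timing.

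This concerns a preliminary secondary outcome in ten infants. The primary safety and comfort outcome is unaffected. The change is worth making, but the trial does not stand or fall on it.

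**What to change.** In Section 16.3, replace the examination of reports with a classification rule fixed before the EarGenie waveforms are looked at, and applied by script to the stored recordings without using the test verdict. The rule should:

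1. name the region or regions, and say how they combine if there is more than one;
2. state exact latency windows and drop *around*;
3. define a combined shape, including what happens when only one of the two extremes falls in its window;
4. set a minimum response size relative to baseline noise.

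Run the same rule on the 36 existing NIRx recordings. Report waveform conformity separately from the significance proportions, with the EarGenie and NIRx rates side by side. State whether 9/10 and 7/10 apply to the test result alone or to result plus waveform, and align the synopsis and Sections 8.2, 12.3 and 16.3 accordingly.

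The cost is a short script and a protocol wording change. Section 14.2.1 already provides for storing the EarGenie recordings, and Section 6.1 says the NIRx infants were tested in the sponsor's own laboratory; that those recordings are still retrievable is assumed. No further infants, visits or readers are needed, and the comparison stays descriptive, in keeping with Section 16.1. The drawback is that a fixed rule may class an unusual but genuine waveform as non-conforming. Such waveforms can still be displayed and described.
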